5.1 Inclusion Criteria

Age

1. Patients must be ≥ 18 years of age at the time of signing the informed consent.

Type of Patient and Disease Characteristics

2. Patients who had a kidney transplant performed ≥ 28 days prior to enrollment.
3. BKV, based on the following criteria (both criteria a and b must be met):
 - a. Any positive whole blood or plasma BK viral load at a local laboratory obtained ≤ 90 days before the start of screening.
 - b. Confirmation of BK viremia of 350 copies/mL – 10,000,000 copies/mL as determined by the central laboratory at screening.
4. At least 1 identified, suitably matched PSL cell line for infusion is available.

Sex

5. Male and/or female

Contraceptive use by men and women should be consistent with local regulations regarding the methods of contraception for those participating in clinical studies.

- a. Male patients:

Male patients are eligible to participate if they agree to the following during the study treatment period and for at least 90 days after the last dose of study treatment:

- Refrain from donating sperm

PLUS, either:

- Be abstinent from heterosexual intercourse as their preferred and usual lifestyle (abstinent on a long term and persistent basis) and agree to remain abstinent

OR

- Must agree to use contraception /barrier as detailed below
 - Agree to use a male condom and should also be advised of the benefit for a female partner to use a highly effective method of contraception as a condom may break or leak when having sexual intercourse with a woman of childbearing potential (WOCBP) who is not currently pregnant b. Female patients:
 - A female patient is eligible to participate if she is not pregnant or breastfeeding, and 1 of the following conditions applies:

- She is a woman of non-childbearing potential (WONCBP) as defined in [Section 10.4.1](#)

OR

- She is a WOCBP and using an acceptable contraceptive method as described in [Section 10.4.2](#) during the study treatment period and for at least 90 days after the last dose of study treatment. The Investigator should evaluate the potential for contraceptive method failure (eg, noncompliance, recently initiated) in relationship to the first dose of study treatment.
- A WOCBP must have a negative highly sensitive serum pregnancy test within 21 days before the first dose of study treatment, see [Section 8.2.5](#).
- Additional requirements for pregnancy testing during and after study treatment are located in [Section 8.2.5](#).
- The Investigator is responsible for review of medical history, menstrual history, and recent sexual activity to decrease the risk for inclusion of a woman with an early undetected pregnancy.

Informed Consent

6. Capable of giving signed informed consent as described in [Section 10.1.3](#) which includes compliance with the requirements and restrictions listed in the informed consent form (ICF) and in this protocol.

5.2 Exclusion Criteria

Medical Conditions

1. Undergone allogeneic hematopoietic cell transplantation.
2. Evidence or history of GVHD or CRS (Appendix 5 [[Section 10.5](#)] and Appendix 6 [[Section 10.6](#)], respectively).
3. Uncontrolled or progressive bacterial or fungal infections (ie, evidence of bacteremia, fungemia, dissemination, and/or organ-specific infection not well controlled by present therapies).
4. Uncontrolled or progressive viral infections (ie, evidence of viremia, dissemination, and/or organ-specific infection not well controlled by present therapies) not targeted by PSL.
5. Uncontrolled or progressive EBV-associated post-transplant lymphoproliferative disorder.
6. Known or presumed pneumonia.
7. Hemodynamic or respiratory instability defined as either of the following:
 - a. Requirement for continuous infusions of inotropes or vasopressors for blood pressure support.
 - b. Requirement for endotracheal intubation or mechanical ventilation.

8. Evidence of any medical condition that in the opinion of the Investigator might interfere with the patient's ability to participate in the trial.

Prior/Concomitant Therapy

9. Ongoing therapy with high-dose systemic corticosteroids (ie, prednisone dose >0.5 mg/kg/day or equivalent).
10. Patients who received, or are planned to receive, abatacept or belatacept, within 3 months of screening, or who received equine anti-thymocyte globulin ([ATG] Atgam®) or rabbit ATG (Thymoglobulin ®) in doses of >4.5 mg/kg or alemtuzumab (Campath-1H) or other immunosuppressive T cell-targeted monoclonal antibodies <28 days prior to randomization.

Prior/Concurrent Clinical Study Experience

11. Receipt of other investigational antiviral treatments (eg, anti-BK monoclonal antibodies) within 28 days or 5 half-lives (whichever is longer) prior to randomization.

Diagnostic assessments

12. Liver dysfunction, defined as liver transaminases (ie, aspartate aminotransferase or alanine aminotransferase) >5 times the upper limit of normal (ULN) or direct bilirubin >2 times the ULN reference per local laboratory.
13. Renal dysfunction, defined as estimated glomerular filtration rate (eGFR) (estimated by Modified Dose in Renal Disease [MDRD] formula) <20 mL/min/1.73 m².

Other Exclusions

14. Pregnant or nursing or planning to become pregnant.
15. ABO incompatible or complement-dependent lymphocytotoxic crossmatch positive transplant (isolated positive B cell crossmatches are not an exclusion criterion).
16. Weight <40 kg.
17. History of hypersensitivity to any of the components of the Investigational Product.

5.3 Lifestyle Restrictions

This section is not applicable.

5.3.1 Meals and Dietary Restrictions

This section is not applicable.

5.3.2 Caffeine, Alcohol, and Tobacco

This section is not applicable.

5.3.3 Activity

This section is not applicable.

5.4 Screen Failures

Screen failures are defined as patients who consent to participate in the clinical study but are not randomized into the clinical study. A minimal set of screen failure information is required to ensure transparent reporting of screen failure patients to meet the Consolidated Standards of Reporting Trials publishing requirements and to respond to queries from regulatory authorities. Minimal information includes demography, screen failure details, eligibility criteria, and any serious adverse events (SAEs). If a matching PSL line is not available, resulting in the patient being a screen failure, the HLA type data will be collected in addition to the minimal information required to meet the Consolidate Standards of Reporting Trials.

Individuals who do not meet the criteria for participation in this study (screen failure) may be rescreened following discussion with, and approval of, the Sponsor.

6 STUDY TREATMENT(S) AND CONCOMITANT THERAPY

Study treatment is defined as any investigational intervention(s), marketed product(s), placebo, or medical device(s) intended to be administered to a study patient according to the study protocol.

6.1 Study Treatment(s) Administered

PSL is a third-party, donor-derived, “off-the-shelf,” Virus-specific T cell product with specificity for BKV, AdV, CMV, EBV, and HHV-6 (with additional cross-reactive specificity for JCV) that is cryopreserved and ready for immediate use. The placebo arm will receive separate IV infusions of cryopreservation media (without cells) as placebo.

For more information, see the Investigator’s Brochure.

PSL cell lines will be checked for cell concentration, viability, identity, phenotype, potency, endotoxin, mycoplasma, and sterility.

Table 3 Study Treatment Information

Arm Name	[REDACTED] [REDACTED]	[REDACTED] [REDACTED]	Placebo
Intervention Name	PSL	PSL	Placebo
Type	Drug	Drug	Drug
Dosage formulation	Ampule (Cryovial)	Ampule (Cryovial)	Ampule (Cryovial)
Unit dose strength(s)	[REDACTED] [REDACTED]	[REDACTED] [REDACTED]	[REDACTED]
Dosage Level(s)	[REDACTED] PSL cells [REDACTED] [REDACTED]	[REDACTED] PSL cells [REDACTED] [REDACTED] [REDACTED] [REDACTED] [REDACTED]	Placebo [REDACTED] [REDACTED]
Route of Administration	IV slow push [REDACTED]	IV slow push [REDACTED]	IV slow push [REDACTED]
Use	Experimental	Experimental	Placebo control
IMP and NIMP	IMP	IMP	IMP
Sourcing	Provided centrally by the Sponsor	Provided centrally by the Sponsor	Provided centrally by the Sponsor
Packaging and Labeling	Study treatment will be provided in cryovials. Each cryovial will be labeled as required per country requirement	Study treatment will be provided in cryovials. Each cryovial will be labeled as required per country requirement	Study treatment will be provided in cryovials. Each cryovial will be labeled as required per country requirement
Current/ Former Name(s) or Alias(es)	Posoleucel/ALVR105, Viralym M	Posoleucel/ALVR105, Viralym M	Not applicable

Abbreviations: IMP = investigative medicinal product; IV = intravenous; Q = every.

6.1.1 Cell Line Selection

PSL cell lines will be selected for each patient based on an overall HLA match [REDACTED]
[REDACTED] as outlined below. The HLA alleles used for evaluation of matching are HLA-A, HLA-B, HLA-DR, and HLA-DQ.

The appropriate study treatment (ie, the cell lines for infusion) for patient administration will be selected [REDACTED]

6.1.2 Study Treatment Administration

Randomization of patients to PSL versus placebo will occur only after cell line matching and selection has been confirmed (to satisfy inclusion criteria).

Premedication is not required, except for patients with a prior history of reaction to blood products. These patients may receive premedication with 0.25 to 0.5 mg/kg (maximum dose of 25 mg) diphenhydramine (IV or oral) and/or 5 to 10 mg/kg (maximum dose of 1000 mg) acetaminophen (IV or oral) prior to study treatment administration. Premedication with corticosteroids is prohibited.

At or close to the time of administration, the product will be thawed. For further details on product preparation prior to infusion, please see the Cell Therapy Manual.

Patients will be monitored according to institutional standards for the administration of blood products and, at a minimum, according to the following requirements:

- Patients in an outpatient setting must remain in the clinic for ≥ 1 hour after the end of the infusion.
- Patients must remain on continuous pulse oximetry for ≥ 30 minutes after the end of the infusion.
- Vital signs will be monitored within 30 minutes prior to the infusion, at the end of infusion, and at 15, 30, 45, and 60 (± 5) minutes after the end of the infusion.

All findings must be recorded in the electronic case report form (eCRF).

Patients will receive supportive care for acute or chronic toxicity, including blood components, antibiotics, or other interventions as appropriate per local treatment guidelines. See [Section 6.8.2](#) for additional information.

If a patient experiences an infusion reaction, 0.25 to 0.5 mg/kg (maximum dose of 25 mg) diphenhydramine (IV or oral) and/or 5 to 10 mg/kg (maximum dose of 1000 mg) acetaminophen

(IV or oral) may be administered as treatment. The maximum recommended single and daily doses of diphenhydramine and acetaminophen should not be exceeded. In the case of suboptimal control of an infusion reaction or the need to use corticosteroids for treatment of an infusion reaction, doses of $\leq 0.5\text{mg/kg/day}$ of prednisone or equivalent should be considered first.

6.2 Preparation/Handling/Storage/Accountability

1. The Investigator or designee must confirm appropriate temperature conditions have been maintained during transit for all study treatment received and any discrepancies are reported and resolved before use of the study treatment.
2. Only patients enrolled in the study may receive study treatment and only authorized site staff may supply or administer study treatment. All study treatments must be stored in a secure, environmentally controlled, and monitored (manual or automated) area in accordance with the labeled storage conditions with access limited to the Investigator and authorized site staff.
3. The Investigator, institution, or the head of the medical institution (where applicable) is responsible for study treatment accountability, reconciliation, and record maintenance (ie, receipt, reconciliation, and final disposition records).
4. Further guidance and information for the final disposition of unused study treatment are provided in the Cell Therapy Manual.

6.2.1 Study Treatment Preparation and Dispensing

PSL and placebo will be supplied in cryovials, which are to be transported from vapor phase liquid nitrogen storage at the clinical site to the cell-thawing and preparation location in a liquid nitrogen dewar or other suitable container. Details of the cell thawing, preparation for dosing, and administration to the patient will be provided to clinical sites in a separate Cell Therapy Manual.

6.2.2 Storage and Accountability

PSL or placebo is stored in the vapor phase of liquid nitrogen in a continuously monitored storage freezer.

All material containing PSL or placebo will be treated and disposed of as hazardous waste in accordance with governing regulations and clinical site procedures.

PSL and placebo accountability are the responsibility of the Principal Investigator and Sponsor. However, this responsibility may be delegated to a suitably qualified Investigator or designee who has had appropriate study-specific training that has been documented. The Sponsor will maintain records that will allow anonymous traceability of each PSL cell line to the third-party PBMC donor from whom it originated. These records will be maintained for 30 years after expiry for each cell line.

Detailed records will be maintained to allow for accurate accountability of PSL and placebo as per applicable Sponsor and clinical site procedures. For further details and specifications, see the Cell Therapy Manual.

6.3 Measures to Minimize Bias: Randomization and Blinding

This study is blinded to safeguard the integrity of the AE determination process, and to ensure that decisions regarding discontinuation of infusions for apparent efficacy are made in an unbiased fashion.

Study using IVRS/IWRS	
All patients will be centrally assigned to randomized study treatment using an Interactive Voice/Web Response System (IVRS/IWRS). Before the study is initiated, the telephone number and call-in directions for the IVRS and/or the log in information and directions for the IWRS will be provided to each site.
 
Study treatment will be dispensed at the study visits summarized in the Schedule of Activities (SOA, Section 1.3).

------------------------------	---

The Sponsor designee (eg, interactive response technology [IRT] vendor) will have a designated randomization administrator who will maintain the randomization codes in accordance with standard operating procedures to ensure the blind integrity is properly maintained. Care should be exercised to ensure that only Sponsor personnel who require knowledge of treatment assignments will be unblinded (eg, staff involved in Suspected Unexpected Serious Adverse Reaction [SUSAR] reporting).

Blind Break (IVRS/IWRS)	
The IVRS/IWRS will be programmed with blind-breaking instructions. In case of an emergency, the Investigator has the sole responsibility for determining if unblinding of a patients' intervention assignment is warranted. Patient safety must always be the first consideration in making such a determination. If the Investigator decides that unblinding is warranted, the Investigator should make every effort to contact the Sponsor prior to unblinding a patient's intervention assignment unless this could delay emergency treatment of the patient. If a patient's intervention assignment is unblinded, the Sponsor must be notified within 24 hours after breaking the blind. The date and reason that the blind was broken must be recorded in the source documentation and case report form, as applicable.

--------------------------------	---

Unblinding should only occur in the event of an emergency or AE for which it is necessary to know the study treatment to determine an appropriate course of therapy. If the patient's study treatment must be unblinded, the Investigator or qualified designee should contact IRT for the study treatment information. The IRT documentation indicating the blind break at the site must be retained with the patient's source documentation in such a way as to avoid unblinding the treatment assignment to other site or Sponsor blinded personnel.

If possible, the Investigator should attempt to contact the Medical Monitor prior to unblinding. If not possible, the Investigator should notify the Medical Monitor as soon as possible of the unblinding without disclosing the treatment assignment of the unblinded patient. The Investigator must document the patient's identification, the reason for breaking the blind, and the date and time for breaking the blind. Following unblinding, the Investigator must withdraw the patient from the study.

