14. A urine pregnancy test will be performed at the site prior to study therapy initiation for patients of childbearing potential. If the result is negative, the patient will be eligible for study treatment administration and the remainder of the Day 1 testing/procedures will be performed. If the urine pregnancy result is positive, the patient must not receive study treatment. An on-site urine pregnancy test will also be performed at Weeks 4, 8, and 12 for patients of childbearing potential who are eligible for dosing. Dosing may only be completed following a negative test.
15. FSH will be tested at screening for women of nonchildbearing potential who are postmenopausal, defined as 12 consecutive months with no menses without an alternative medical cause.

16. Randomization will occur after all screening procedures are complete, after all eligibility criteria are met, and prior to study treatment administration. Randomization will mark the end of the screening period. Patients who meet all of the inclusion criteria and none of the exclusion criteria will be randomized to receive sequential infusions of PSL cells or placebo.
17. Patients will receive infusions of either PSL or placebo after all blood drawing procedures listed for their visit in the SoA. Patients in the active treatment arms will receive the same [REDACTED] cells dose for all infusions. Placebo infusions will be administered as appropriate to maintain the blind. As GVHD and CRS are a theoretical safety concern, the incidence and severity of GVHD and CRS will be monitored during the study. No patients are permitted to receive an infusion of PSL or placebo if they develop GVHD (\geq Stage 1; see Appendix 5, [Section 10.5](#)) or CRS $>$ Grade 2. If any patient develops GVHD or CRS $>$ Grade 2, study treatment infusions should be stopped immediately, and the patient treated per standard of care.

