2.4.2 Potential Risks

PSL primarily targets cells infected with AdV, BKV (and/or JCV), CMV, EBV, and/or HHV-6. The main risks of administration are inflammation at sites of disease or GVHD due to cross reactivity with the recipient's HLA antigens. Adverse events attributable to virus-specific T cell administration may potentially occur in a small percentage of the treated population. These can include both hematologic and non-hematologic effects, as reported in the CHARMs study.

Studies of donor-derived virus-specific T cells suggest that virus-specific T cells do not persist in patients who receive methylprednisolone in doses \geq 1 mg/kg/day. Therefore, if patients develop severe inflammatory reactions thought to be attributable to PSL, a therapeutic option is to administer methylprednisolone (1 to 2 mg/kg/day). In patients who develop skin rash or skin GVHD, excellent responses have been seen with administration of topical steroids.

As with other biological therapies delivered by IV infusion, possible side effects of PSL infusion include allergic reaction (anaphylaxis), decreased oxygenation, nausea/vomiting, arrhythmia, and hypotension.

A detailed breakdown of the time points for blood sample collection during the course of this study is provided in [Section 1.3](#).

In order to minimize the volume of blood collected during the study, the blood volume of individual samples has been reduced to the maximum extent feasible. This has been done in a manner that is expected to maintain the scientific integrity of the study while minimizing the risks to patients.

No single blood draw will exceed approximately 72 mL, and the total blood volume collected during the first 8 weeks of the study will be approximately 280 mL (~4 mL/kg for a 70 kg patient). Over the entire 26-week course of the study, the total blood volume collected is outlined in the laboratory manual.

For the collection of other study-related material from patients, there are no invasive procedures that are required for the study conduct beyond those procedures being used for the routine clinical care of these patients.

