7 DISCONTINUATION OF STUDY TREATMENT AND PATIENT DISCONTINUATION/WITHDRAWAL

7.1 Discontinuation of Study Treatment

The following criteria do not necessitate withdrawal from the study, but do render the patient ineligible to receive any additional infusions of study treatment:

1. Development of \geq Grade 1 acute GVHD within 6 weeks, or a Grade 3 to 4 non-hematologic AE within 4 weeks from last PSL dose that is considered related to study treatment administration. If this occurs, the patient's toxicities will be followed until resolution or until the patient's participation in the study ends.
2. Receipt of any other hematopoietic stem cell product.
3. Receipt of therapy for new malignancy.
4. Occurrence of Grade 3 or 4 CRS. If this occurs, the patient's toxicities will be followed until resolution or until the patient's participation in the study ends.
5. Requirement for prohibited concomitant medication
6. Pregnancy

If any of the above criteria are met, every effort should be made to keep the patient in the study and continue follow-up.

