7.2 Patient Discontinuation/Withdrawal from the Study

Participation of a patient in this clinical study may be discontinued for any of the following reasons:

- The patient withdraws consent
- The patient requests discontinuation from the study for any reason
- Occurrence of any medical condition or circumstance that exposes the patient to substantial risk and/or does not allow the patient to adhere to the requirements of the protocol
- Any SAE, clinically significant AE, severe laboratory abnormality, intercurrent illness, or other medical condition that indicates to the Investigator that continued participation is not in the best interest of the patient
- Patient failure to comply with protocol requirements or study-related procedures
- Termination of the study by the Sponsor or the regulatory authority

If a patient withdraws prematurely from the study due to the above criteria or for any other reason, study staff should make every effort to complete the full panel of assessments scheduled for the Week 24 (Day 169) Visit. The reason for patient withdrawal must be documented in the eCRF.

If the patient withdraws consent for disclosure of future information, the Sponsor may retain and continue to use any data collected before such a withdrawal of consent.

If a patient withdraws from the study, he/she may request destruction of any samples taken and not tested, and the Investigator must document this in the site study records.

Withdrawn patients will not be replaced.

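### Protocol 6.3 makes an Investigator blind break end study participation, which conflicts with 7.1 when a toxicity is the trigger and cuts safety follow-up short

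*Protocol*

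**What the plan says.** Protocol 6.3 gives the decision to unblind in an emergency to the Investigator: "In case of an emergency, the Investigator has the sole responsibility for determining if unblinding" is warranted. It limits the trigger: "Unblinding should only occur in the event of an emergency or AE for which it is necessary to know the study treatment" in order to choose therapy. It then states the consequence: "Following unblinding, the Investigator must withdraw the patient from the study". That means leaving the study, not only stopping infusions. The point here is this Investigator blind break, not the unblinded Sponsor staff who handle SUSAR reporting.

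Protocol 7.1 lists events that end study treatment, including acute GVHD, related Grade 3 to 4 non-hematologic events and Grade 3 or 4 CRS. It opens with "The following criteria do not necessitate withdrawal from the study" and closes by saying that, if any criterion is met, "every effort should be made to keep the patient in the study and continue follow-up".

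Protocol 7.2 lists reasons for leaving the study. Unblinding is not named, although the list is open. For anyone who leaves early, "study staff should make every effort to complete the full panel of assessments scheduled for the Week 24 (Day 169) Visit". Withdrawn patients are not replaced.

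**The concern.** A blind break is allowed only for an emergency or an adverse event, so its triggers can be the same toxicities that 7.1 lists. For such a patient one section orders withdrawal and the other asks the site to keep following. Neither section refers to the other, and no rule of precedence appears in the Protocol or the SAP.

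The stake is the primary endpoint. Protocol 9.4.5 counts treatment-emergent events through the Week 24 visit, while Protocol 8.3.1 ends routine collection when participation ends. Follow-up would therefore be shortened in patients chosen by a safety event. The adverse event tables in SAP 3.5 and 3.5.1 are numbers and percentages of patients. A withdrawn patient stays in the denominator, and new non-serious events after withdrawal are no longer collected.

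**Working it through.** **1. The two instructions side by side.** Take a patient with Grade 3 CRS whose blind is broken to guide care. Section 7.1 says to stop infusions and keep following. Section 6.3 says to withdraw from the study. Section 7.1 makes no exception for unblinded patients, and 6.3 makes none for 7.1 events.

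**2. How likely the overlap is.** Footnote 17 to the Schedule of Activities lowers the need to unblind for GVHD or CRS above Grade 2. On either arm, "study treatment infusions should be stopped immediately, and the patient treated per standard of care". Overlap is still possible, because Protocol 2.4.2 describes a treatment option "if patients develop severe inflammatory reactions thought to be attributable to PSL", where knowing the assignment could matter.

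**3. What is kept after withdrawal.**
- The patient stays in the Safety Population (SAP 3.2.3), and the triggering event stays in the tables (SAP 3.5.1).
- SAEs and events of special interest are followed to outcome (Protocol 8.3.3, 10.3.4).
- Related SAEs that the Investigator learns of later are still reported (8.3.1), and pregnancies are followed to outcome (8.3.5).
- One early termination panel is attempted (7.2).

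**4. What is lost.** Active collection of new events and the remaining scheduled visits are lost. Follow-up of a non-serious event that is not of special interest can also end with participation.

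**5. Size per affected patient.** The day of the blind break is an assumption. That day's visit is taken as done, followed by one early termination panel. From the Schedule of Activities:
- Planned follow-up: 169 − 1 = 168 days.
- BK loads: Weeks 2, 4, 6, 8, 10, 12, 14, 16, 18, 20, 22, 24 = 12.
- Clinical labs: Weeks 2, 4, 6, 8, 10, 12, 16, 20, 24 = 9.
- Donor-specific antibodies (DSA): Weeks 12, 24 = 2.

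| Lost | Blind break at Day 29 | Blind break at Day 85 |
|---|---|---|
| Days | 169 − 29 = 140; 140/168 = 83% | 169 − 85 = 84; 84/168 = 50% |
| BK loads | 10 − 1 = 9; 9/12 = 75% | 6 − 1 = 5; 5/12 = 42% |
| Lab visits | 7 − 1 = 6; 6/9 = 67% | 3 − 1 = 2; 2/9 = 22% |
| DSA samples | 2 − 1 = 1; 1/2 = 50% | 1 − 1 = 0; 0/2 |

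Share of planned patient-days lost through one such patient:
- 20-patient arm: 140/(20 × 168) = 4.2%; 84/(20 × 168) = 2.5%.
- 40 pooled PSL patients: 140/(40 × 168) = 2.1%; 84/(40 × 168) = 1.3%.

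**6. Where the early panel goes in the analysis.** SAP 3.1.2 assigns early termination visits by study day. Under Appendix B, a panel counts as Week 24 only from Day 163 (BK) or Day 156 (labs). A panel on Days 30 to 36 falls in the Week 4 window (Days 23 to 36) for both. The Day 29 sample, being on target, would then be the one used. The table above therefore counts samples collected; in the by-visit BK summary, 10 of 12 visits would be empty. The panel still reaches the listings. Appendix B has no DSA window, so how an early DSA sample enters the by-visit DSA summary in SAP 3.4.2 is not stated.

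**7. Missing data.** SAP 3.1.5 analyzes data as observed in general. Its imputation rules cover dates and values below quantification. For missed assessments the only imputation is the last-observation-carried-forward sensitivity analysis of BK viremia (SAP 3.4.2, 3.5.2). Nothing covers missed eGFR or DSA.

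**The case against.** The best reply is that the sections can be read together. Section 7.1 says only that the toxicity does not itself require withdrawal, while 6.3 adds a separate trigger in mandatory terms, and mandatory wording outranks best efforts. Section 7.1 also foresees participation ending before a toxicity resolves. That reading is possible, but no passage states it, and the retention instruction in 7.1 applies whenever any criterion is met. Even under that reading, 6.3 still ends follow-up early.

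The other replies stand in part:
- GVHD, CRS and serious events are still followed to outcome, so for the triggering event itself the gap is mainly a non-serious related Grade 3 to 4 event that is not of special interest. The larger loss is new events.
- Frequency is unknown, and the narrow unblinding criterion suggests it is low.
- Patient-days correspond to no planned table, so those percentages only indicate scale. The laboratory shift table uses the worst post-baseline value, and BK resolution is also summarized at any visit, so an early panel is not wasted.
- Section 6.3 aims to protect adverse event determination, and reports made after unblinding are more open to bias. That supports flagging such data. It is a weak reason to stop collecting them, since BK load, creatinine-based eGFR and DSA are objective laboratory measures.

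**Conclusion.** The concern holds. For a patient who is unblinded because of a 7.1 event, the Protocol gives opposing instructions with no precedence. Whichever section was meant to govern, following 6.3 as written ends active event collection and scheduled visits early in patients selected by an emergency or adverse event.

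For the two assumed timings, the loss per patient is 50% to 83% of follow-up days and 42% to 75% of post-baseline BK loads, net of one early panel. With 20 patients per arm and no replacement, one such patient is 1/20 = 5% of an arm. The documents give no expected number of blind breaks and it may be small, so this should be corrected but does not by itself undermine the trial. Follow-up of the triggering SAE or event of special interest is not lost.

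**What to change.** Reconcile Protocol 6.3, 7.1 and 7.2 so that an Investigator blind break alone does not end study follow-up or data collection. Scheduled assessments would continue through Week 24 unless consent is withdrawn or another 7.2 reason applies. Whether study treatment continues after unblinding is for the sponsor to reconcile; no rule is proposed here.

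Add one SAP sentence: data collected after unblinding are included in the Safety and ITT analyses and flagged as such. Inclusion partly follows from the existing population definitions; the flag is new.

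The cost is a short Protocol clarification, with the IRB/IEC approval that Protocol 10.1.1 requires for amendments, and the SAP sentence. The visits are already scheduled. The downside is that later adverse event reports in a few patients would not be blinded, which is the reason for the flag.
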